2 STUDY OBJECTIVES

2.1 Primary Objective

- To evaluate plasma safinamide pharmacokinetic parameters after single and multiple dose administration of the investigational products.

2.2 Secondary Objective

- To collect safety and tolerability data after single and multiple dose administration of the investigational products.

3 INVESTIGATIONAL PLAN

3.1 Overall Study Design and Plan

This is a Phase I, single center, single and multiple-dose, open-label, randomized, parallel-group, pharmacokinetics, safety and tolerability study.

The study population will consist of 24 adult healthy male and female subjects (12 per cohort). Subjects will be randomized to two study cohorts to receive single and multiple doses of 50 mg safinamide (cohort 1), or single and multiple doses of 100 mg safinamide (cohort 2), according to the study randomized, parallel-group design, as follows:

| Cohort | Period 1 - single dose | | Washout | Period 2 - Multiple doses | |
|----------|------------------------|--|---------|---------------------------|--|
| | Day 1 | | | Days 8 - 14 | |
| Cohort 1 | 50 mg po | | 7 days | 50 mg po o.d for 7 days | |
| Cohort 2 | 100 mg po | | | 100 mg po o.d. for 7 days | |

3.2 Endpoints and Associated Variables

3.2.1 Efficacy Variables

Not applicable.

3.2.2 Pharmacokinetic Variables

Unless otherwise stated, derivation of Pharmacokinetic (PK) parameters will be the responsibility of Qualitative Clinical Development (QCD), PAREXEL International. The following PK parameters will be determined for Investigational Medicinal Product (IMP) in plasma following single dose and multiple dose administration:

Table 1 Pharmacokinetic Parameters after Single Dose Administration

| Parameter | Definition |
|--------------------|---|
| C_{\max} [1] | Maximum observed concentration |
| t_{\max} [1] | Time corresponding to occurrence of C_{\max} |
| $t_{1/2}$ | Apparent terminal elimination half life |
| C_{last}/C_t | Last quantifiable concentration |
| AUMC | Area under the first moment of the concentration-time curve |
| K_{el} | Terminal elimination rate constant |
| $AUC_{(0-t)}$ [1] | AUC from time zero to the last quantifiable concentration |
| $AUC_{(0-24)}$ [1] | AUC over the dosing interval (24 hours) |
| $AUC_{(0-\infty)}$ | AUC from time zero extrapolated to infinity |
| % AUC_{ex} | Percentage of $AUC_{(0-\infty)}$ obtained by extrapolation |
| MRT | AUMC/AUC |
| CL/F | Apparent clearance following oral administration |
| V_d/F | Apparent volume of distribution during terminal phase |

[1] These parameters will also be calculated after first multiple dose (day 8).

Table 2 Pharmacokinetic Parameters after Multiple Dose Administration

| Parameter | Definition |
|---------------------|---|
| $C_{\max,ss}$ | Maximum observed concentration at steady state |
| $C_{\min,ss}$ | Minimum observed concentration at steady state |
| $t_{\max,ss}$ | Time corresponding to occurrence of $C_{\max,ss}$ at steady state |
| $K_{el,ss}$ | Terminal elimination rate constant at steady state |
| $AUC_{(0-t),ss}$ | AUC to last observed concentration at steady state |
| $AUC_{(0-\tau),ss}$ | AUC over the dosing interval at steady state |
| CL/F_{ss} | Apparent clearance following oral administration at steady state |
| V_d/F_{ss} | Apparent volume of distribution during terminal phase at steady state |
| $C_{ave,ss}$ | Average concentration at steady-state |
| DF% | Peak trough fluctuation |
| $R_{acc,AUC}$ | Accumulation ratio, based on AUC |
| $R_{acc,C_{\max}}$ | Accumulation ratio, based on C_{\max} |

Pharmacokinetic Parameter Calculation Methods

PK parameters will be calculated by non-compartmental analysis methods from the concentration-time data using WinNonlin (WNL) Professional (Version **8.0**) following these guidelines:

- Actual sampling times relative to dosing rather than nominal times will be used in the calculation of all derived PK parameters.
- There will be no imputation of missing data. Any subjects with missing concentration data will be included in the PK analysis set provided that at least one PK parameter can be reliably calculated.
- Single dose: All below the limit of quantification (BLQ) values pre-dose and in the absorption phase prior to the first quantifiable concentration will be substituted by zeros. Thereafter BLQ values between evaluable concentrations will be substituted by missing before the calculation of the PK variables. Terminal BLQ values will be disregarded.

- Multiple dose: For Day 1, all BLQ values pre-dose and in the absorption phase prior to the first quantifiable concentration will be substituted by zeros. For subsequent dosing days not separated by a washout, BLQ values pre-dose, in the absorption phase, and between evaluable concentrations will be substituted by missing, before the calculation of the PK variables. Terminal BLQ values will be disregarded.

PK parameters will be estimated according to the following guidelines:

For single dose

- C_{max} will be obtained directly from the concentration-time data.
- t_{max} is the time at which C_{max} is observed.
- K_{el} will be estimated at terminal phase by linear regression after log-transformation of the concentrations:
 - Only those data points that are judged to describe the terminal log-linear decline will be used in the regression.
 - A minimum number of three data points in the terminal phase will be used in calculating K_{el} with the line of regression starting at any post- C_{max} data point (C_{max} should not be part of the regression slope) and including C_{last} , t_{last} .
 - The adjusted correlation coefficient (R^2 adjusted) in general should be greater than 0.80. Any value less than 0.80 may be used at the PK Scientist's best knowledge and judgment.
 - An appropriate number of decimal places should be used for K_{el} to enable the reported value of $t_{1/2}$ to be calculated.
- $t_{1/2}$ will be calculated as $\ln 2 / K_{el}$.
- AUC is calculated as follows:
 - The linear trapezoidal method will be employed for all incremental trapezoids arising from increasing concentrations and the logarithmic trapezoidal method will be used for those arising from decreasing concentrations.
 - $AUC_{(0-t)} = \int_0^t C(t) dt$.
 - $AUC_{(0-\infty)} = \int_0^t C(t) dt + \int_t^\infty C(t) dt = AUC_{(0-t)} + C_t / K_{el}$.
 - C_t is last observed quantifiable concentration.
- %AUC_{ex} will be calculated as $(1 - [AUC_{(0-t)} / AUC_{(0-\infty)}]) \times 100$.

- CL/F will be calculated as dose/AUC_(0-inf), parent drug only.
- V_d/F will be calculated as (CL/F)/Kel, parent drug only.

For multiple dose

- C_{max,ss} at steady state will be obtained directly from the concentration-time data.
- C_{min,ss} at steady state will be obtained directly from the concentration-time data.
- t_{max,ss} time at which C_{max,ss} occurs at steady state.
- K_{el,ss} will be estimated at terminal phase by linear regression
 - Only those data points that are judged to describe the terminal log-linear decline will be used in the regression.
 - A minimum number of three data points in the terminal phase will be used in calculating K_{el,ss} with the line of regression starting at any post-C_{max,ss} data point (C_{max,ss} should not be part of the regression slope) and including C_{last}, t_{last}.
 - The adjusted correlation coefficient (R² adj) in general should be greater than 0.80. Any value less than 0.80 may be used at the PK Scientist's best knowledge and judgment.
 - An appropriate number of decimal places should be used for K_{el,ss} to enable the reported value of t_{1/2,ss} to be calculated AUC_{0-24,ss}
- Area under the concentration-time curve over the dosing interval will be calculated using linear trapezoidal method; all incremental trapezoids arising from increasing concentrations and the logarithmic trapezoidal method will be used for those arising from decreasing concentrations.
- CL /F_{ss} Apparent clearance following oral administration at steady state for the parent drug calculated as dose/ AUC_(0-24,ss).
- V_d /F_{ss} Apparent volume of distribution during terminal phase at steady state for the parent drug calculated as (CL/F_{ss})/ Kel_{ss}.
- C_{avg,ss} Average steady-state concentration calculated as AUC_{(0 τ),ss}/τ.

The following PK parameters will also be derived using Statistical Analysis Software (SAS®) (version 9.3 or higher).

- DF% Peak trough fluctuation calculated as $100 * (C_{\max,ss} - C_{\min,ss}) / C_{\text{avg},ss}$.
- $R_{\text{acc,AUC}}$ and $R_{\text{acc,Cmax}}$ Accumulation ratio calculated as:
 $C_{\max} \text{ (last dose interval)} / C_{\max} \text{ (first dose interval)}$.
 $AUC_{(0-\tau),ss} \text{ (last dose interval)} / AUC_{(0-24)} \text{ (first dose interval)}$.

3.2.3 Safety Variables

3.2.3.1 Adverse Events

An adverse event (AE) is defined as any untoward medical occurrence in a study subject administered an IMP and which does not necessarily have a causal relationship with this treatment. An AE can therefore be any unfavorable and unintended sign (including a clinically significant abnormal laboratory finding), symptom, or disease temporally associated with the use of an IMP, whether or not considered related to the medicinal product. Adverse events may include the onset of new illness and the exacerbation of pre-existing conditions.

Other untoward events occurring in the framework of a clinical study will be recorded as AEs, e.g. those occurring during treatment-free periods (including Screening or post-treatment Follow-up periods), in association with study-related procedures and assessments.

Concomitant illnesses, which existed before entry into the clinical study, will not be considered AEs unless they worsen during the treatment period. Pre-existing conditions will be recorded as part of the subject's medical history.

All AEs will be coded using the Medical Dictionary for Regulatory Activities (MedDRA) version 22.0.

AEs will be classified as pre-treatment AEs (PTAEs) and treatment-emergent AEs (TEAEs) according to the period of occurrence. A PTAE is defined as an AE occurring before the first dose of investigational product and not worsening after the first dose of investigational product. A TEAE is defined as an AE that occurring or worsening after the first dose of investigational product. Where dates are missing or partially missing, adverse events will be assumed to be treatment-emergent, unless there is clear evidence (through comparison of partial dates) to suggest that the adverse event started or worsen in severity prior to the first dose of study treatment.

Any AEs with incomplete start and end dates/times will be treated as follows:

Adverse events with completely unknown start dates will be considered as treatment-emergent for the tabulations and will be shown as NK in the listings (where NK = Not Known). Partially complete AE dates will not be imputed in the listings and the available day, month and year components will be used to determine if an adverse event is treatment-emergent taking the first dosing date and end of study date as references.

The severity of an AE will be evaluated by the investigator and recorded in the eCRF as Mild, Moderate, or Severe. The investigator will also perform an evaluation with respect to seriousness and causality (relationship of any AE to IMP, whether believed by the investigator to be related or unrelated to the IMP) of the AEs and record it on the appropriate section of the eCRF.

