13.5 Safety and tolerability evaluation

13.5.1 Adverse events

Adverse events (AEs) will be coded by System Organ Class (SOC) and Preferred Term (PT), using the Medical Dictionary for Regulatory Activities (MedDRA).

AEs will be classified as pre-treatment AEs (PTAEs) and treatment-emergent AEs (TEAEs), according to the period of occurrence, as follows:

- PTAEs: all AEs occurring before the first dose of investigational product and not worsening after the first dose of investigational product.
- TEAEs: all AEs occurring or worsening after the first dose of investigational product

Individual PTAEs and TEAEs will be listed in subject data listings. No summary table will be provided for PTAEs. TEAEs will be summarised by treatment and overall. The number and percentage of subjects with any TEAE and the number of TEAEs will be tabulated by SOC and PT, seriousness, relationship with investigational product and severity.

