4.11.1 Adverse Events

All AE data will be listed individually by subject. Only TEAEs will be included in the summary tables. Any PTAEs will be included in the data listings but will not be included in the summary tables of AEs.

AEs will be summarized on per-subject basis and per-event basis. A per-subject basis means that even if a subject reported the same event repeatedly (i.e., events mapped to the same PT) during the trial period, the event will be counted only once. A per-event basis will report the number of events.

An overview table will be summarized for the following categories:

- Any TEAEs
- Any TEAEs related to study drug
- Any severe TEAEs
- Any severe TEAEs related to study drug
- Any TEAEs leading to drug interruption
- Any TEAEs leading to drug withdrawal
- Any TEAEs with outcome of death
- Any TEAEs with outcome of death, related to study drug
- Any SAEs (including events with outcome of death)

- Any SAEs (including events with outcome of death), related to study drug
- Any SAEs leading to drug withdrawal

The following summaries will be produced:

- A summary of TEAEs by SOC, and PT
- A summary of TEAEs by PT
- A summary of the most common TEAEs by PT (reported by > 5% of subjects in any treatment cohort).
- A summary of TEAEs by seriousness, SOC and PT
- A summary of TEAEs by severity, SOC and PT
- A summary of TEAEs by causality, SOC and PT

AE summaries will be displayed by period (single dose and multiple dose) and ordered in terms of decreasing frequency in total column for SOC and PT within SOC, and then alphabetically by SOC and PT within SOC. For each subject and each adverse event, the worst severity recorded will be attributed and used in the by-severity summary. Similarly, the worst seriousness will be attributed and used in the by seriousness summary, the worst causality (most related to treatment) will be attributed and used in the by-causality summary. If severity, seriousness or causality is missing, no imputation will be applied.

A by-subject listing of all adverse events (including non-treatment-emergent events) will be provided. This listing will include: subject identifier, age, sex, ethnicity, treatment cohort, period, adverse event (SOC, PT, and verbatim term), start date, end date, severity, causality, seriousness, action taken, and outcome.

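### For adverse events with missing or partial dates, the SAP's exception to the treatment-emergent default rests on pre-dose onset alone and conflicts with the TEAE and pre-treatment AE definitions

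*SAP*

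**What the plan says.** Protocol v3.0 section 13.5.1 sorts adverse events into two classes. The pre-treatment class is "PTAEs: all AEs occurring before the first dose of investigational product and not worsening after the first dose of investigational product". The other is "TEAEs: all AEs occurring or worsening after the first dose of investigational product". SAP v2.0 section 3.2.3.1 repeats both: a pre-treatment event must occur before the first dose "and not worsening after the first dose of investigational product", and "A TEAE is defined as an AE that occurring or worsening after the first dose of investigational product".

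The same SAP paragraph then gives the rule for incomplete dates: "Where dates are missing or partially missing, adverse events will be assumed to be treatment-emergent, unless there is clear evidence". That evidence is to come from comparing partial dates, and it must be evidence "to suggest that the adverse event started or worsen in severity prior to the first dose of study treatment". The next paragraph adds that "Adverse events with completely unknown start dates will be considered as treatment-emergent for the tabulations", and that for partial dates the available day, month and year are compared with the first dosing date and the end-of-study date. It does not mention worsening.

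SAP section 4.11.1 sets the reporting: "Only TEAEs will be included in the summary tables". Events that are not treatment-emergent appear in the listing only.

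**The concern.** The definitions give an event two routes to treatment-emergent status: it began after the first dose, or it worsened after the first dose. The exception for incomplete dates keeps only the first route. An event that clearly began before dosing and then worsened on drug meets the TEAE definition, yet it loses the default. It cannot be a pre-treatment event either, because it worsened after dosing, so the literal rule leaves it in neither class.

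At stake are the AE summary tables in SAP section 4.11.1: the overview and the tables by system organ class and preferred term, seriousness, severity and causality. Safety and tolerability are the secondary objective, and for the affected events the loss understates them.

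Such events can be foreseen. Protocol section 14.8 starts AE monitoring at informed consent, and section 9.1 opens screening at day -14. SAP section 3.2.3.1 also treats an illness present before entry as an AE only if it worsens during treatment. If the site enters the illness's own onset date, that date is before dosing and may well be partial.

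**Working it through.** The plan states no figure here, so the check compares the definition with the literal rule, pattern by pattern.

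**Inputs.** The definitions come from protocol section 13.5.1 and SAP section 3.2.3.1. The default, the exception and the unknown-date rule come from SAP section 3.2.3.1. The cohort size of 12 (24 in total) comes from SAP section 3.1.

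**Step 1: reduce the exception.** Worsening before the first dose implies onset before the first dose. So the condition (started before, or worsened before) is the same as (started before).

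**Step 2: list the patterns.** Each event is described by onset (before or after the first dose), worsening before it (yes or no), worsening after it (yes or no), and date status (complete; partial and clearly pre-dose; partial and unclear; unknown).

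- Onset before dosing: 2 × 2 × 4 = 16 patterns.
- Onset after dosing: worsening before dosing and a clearly pre-dose date are both impossible, so 1 × 2 × 3 = 6 patterns.
- Total: 16 + 6 = 22.

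**Step 3: compare.** All 6 patterns with onset after dosing agree. For onset before dosing:

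| Worsened after first dose? | Date status | By definition | By literal rule |
|---|---|---|---|
| No | Complete | Pre-treatment | Pre-treatment |
| No | Partial, clearly pre-dose | Pre-treatment | Pre-treatment |
| No | Partial and unclear, or unknown | Pre-treatment | Treatment-emergent |
| Yes | Complete | Treatment-emergent | Treatment-emergent |
| Yes | Partial, clearly pre-dose | Treatment-emergent | **Not treatment-emergent** |
| Yes | Partial and unclear, or unknown | Treatment-emergent | Treatment-emergent |

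Each row covers events with and without worsening before dosing. The row in bold is therefore 2 patterns wrongly excluded. The third row is 2 × 2 = 4 patterns wrongly included, which is the cautious default working as intended.

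**Step 4: test the corrected clause.** If the exception also requires that no worsening on or after the first dose is recorded, the wrongly excluded patterns fall from 2 to 0. The 4 cautious inclusions are unchanged.

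**Step 5: size.** One subject is 1/12 = 8.3% of a cohort, or 1/24 = 4.2% overall. SAP section 4.11.1 lists a preferred term among the most common TEAEs when more than 5% of subjects in any cohort report it. Since 8.3% exceeds 5%, a term reported by one subject qualifies, and losing that subject would remove it.

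**The case against.** The strongest reply is that the sentence only withdraws a presumption. It does not say the event becomes pre-treatment, and the definition could still be applied once the default falls away. The wording might also be meant to mirror the two limbs of the definition, so that whichever of onset or worsening is in question is dated before dosing. Both readings are possible. They show that the text is ambiguous and supports two codings, but they do not settle which one is used: the following paragraph also refers only to date components, and the section 1 introduction says the SAP outlines the programming specifications.

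A second reply concerns how the data are recorded. Protocol section 14.2 counts worsening of a condition present at the start of the trial as an AE. If a worsening is entered as its own record with its own start date, that record is treatment-emergent and nothing is lost. The documents do not say how it is entered, so this stands as a condition on the concern.

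A third reply is that the trigger is remote. Subjects are checked at screening and on day -1 and are confined to day 18. For an event beginning after consent, a missing day clearly shows pre-dose onset only if the recorded month precedes the month of dosing. This also stands.

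A reader might infer that every event beginning before dosing and worsening on drug disappears from all safety tables. The documents do not support that. Completely dated events follow the definition, and unclear or unknown dates default to treatment-emergent. Laboratory, vital-sign and body-weight summaries do not depend on this rule. The full AE listing keeps the event, and the listings in SAP section 4.11.2 (serious events, deaths, and events leading to interruption, withdrawal or discontinuation) are not restricted to TEAEs.

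**Conclusion.** The conflict is real and narrow. The exception ignores worsening on drug, against the definitions in the same SAP section and in protocol section 13.5.1. Read literally, it misclassifies 2 of 22 patterns by exclusion, both with a clearly pre-dose partial date and worsening after dosing. The pattern count describes the logic of the rule and is not an estimate of frequency.

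The consequence is limited to the AE summary tables and rests on three assumptions: the literal reading is the one programmed, the date is incomplete but clearly pre-dose, and the worsening has no separate record. When all three hold, one affected subject is 8.3% of a cohort of 12 for the row concerned, provided all 12 are dosed and the subject has no other TEAE counted in that row.

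A reader might also infer that the missing-date rules as a whole understate adverse events. They do not: the default leans towards inclusion, and only this exception runs the other way. In a descriptive study with no hypothesis test, this is a minor correction that is worth making because it costs almost nothing.

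**What to change.** Reword the sentence in SAP section 3.2.3.1 so that an event with a missing or partial date is taken as treatment-emergent unless the available date components clearly show that it started before the first dose and no worsening on or after the first dose is recorded.

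The second condition should refer to what is recorded and not to partial dates. Dates can show when an event began but cannot show that it did not worsen. Asking them to do so would make the exception almost impossible to meet and would push unchanged pre-dose events into the TEAE tables.

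The cost is one clause in the SAP and one condition in the programming. It would also help to state whether a worsening is entered as a new AE record, since that decides whether the problem can arise at all.

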14.8 AEs monitoring window

- Start of monitoring: from immediately after the signature of the informed consent
- End of monitoring: up to final study visit/ETV (observation window)

An AE occurring after the final visit/ETV and coming to knowledge of the investigator (e.g. during a follow-up assessment or by spontaneous reporting by study subjects) must be recorded only if it is an ADR, according to the investigator’s judgment.

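### SAP v2.0 section 3.2.3.1 has two overlapping missing-date rules for adverse events; read literally, the specific one counts an event that ended before the first dose as treatment-emergent

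*SAP*

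**What the plan says.** SAP v2.0 section 3.2.3.1 classifies adverse events by timing. The definition is "A PTAE is defined as an AE occurring before the first dose of investigational product and not worsening" after that dose; an event that occurs or worsens after the first dose is a TEAE.

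Two rules for missing dates follow.

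- **General rule.** Where dates are missing or partly missing, the event is assumed to be treatment-emergent "unless there is clear evidence (through comparison of partial dates) to suggest that the adverse event started or worsen in severity" before the first dose.
- **Specific rule.** Under a lead-in about events with incomplete start and end dates or times, "Adverse events with completely unknown start dates will be considered as treatment-emergent for the tabulations".

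A further sentence deals with partial dates, "taking the first dosing date and end of study date as references".

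Section 4.11.1 shows PTAEs only in the listings, keeps them out of the summary tables, and displays the AE summaries separately for the single-dose and multiple-dose periods. In Protocol v3.0, section 14.8 gives "Start of monitoring: from immediately after the signature of the informed consent", so events before dosing are collected. Section 13.5.1 of the Protocol gives the same PTAE and TEAE definitions and no missing-date rule.

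**The concern.** The specific rule classifies on the start date alone. If that is unknown, the event becomes a TEAE whatever the end date shows. Yet an event known to have ended before the first dose must have started before it, and, having ended, cannot have worsened after it. That is a PTAE by the SAP's own definition. The general rule might rescue the case, but the SAP does not say whether it applies once the specific rule has been triggered. Two programmers following the text could classify the same record differently.

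At stake is the accuracy of the TEAE tables, where a pre-drug event could be counted as emerging on drug. A second, smaller matter is that an unknown-start TEAE must go into one of two period columns, and no rule in the documents says which.

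**Working it through.** The plan gives no figure to reproduce. The check sets the rules side by side on one illustrative record and then sizes the effect.

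**Test record (illustration).** An event is reported at the Day -1 check with start date unknown and end date Day -3. First dose is on Day 1.

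1. *Definition (SAP 3.2.3.1).* The event ended before the first dose, so it occurred before it and could not worsen after it. Result: PTAE, listing only.
2. *Specific rule (SAP 3.2.3.1).* The start date is completely unknown and the rule has no condition. Result: TEAE, in the tables.
3. *General rule (SAP 3.2.3.1).* An end date of Day -3 implies a pre-dose start. If that counts as clear evidence, the result is PTAE. There is some doubt, because the parenthesis speaks only of comparing partial dates and the test is worded on start or worsening, not on ending.
4. *Medication rule (SAP 4.8), for contrast.* A medication with missing dates is taken as concomitant unless there is clear evidence that it stopped before the first dose. The same dates on a medication record would give: prior. The stop date is tested explicitly.

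Steps 1 and 2 contradict each other. Step 3 can resolve the conflict only if the general rule prevails, which the text does not say.

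**The lead-in.** Read strictly, it confines the specific rule to events whose start and end are both incomplete. A complete end date of Day -3 would then fall outside it. The problem remains for partial end dates. Suppose, for illustration, that the first dose is on the 5th of a month, the start is unknown and the end is known only as the previous month. The event clearly ended before dosing, and the specific rule still makes it a TEAE.

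**Period column.** SAP 4.2 defines the periods and 4.11.1 tabulates by them. The partial-date sentence refers only to the first dosing date and the end of study, not to the Day 8 dose. Nothing else in the documents assigns a period to a TEAE with no start date.

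**Size.** SAP 3.1 plans 12 subjects per cohort, 24 in total. Assume that all are dosed and that the affected subject has no other event on that line.

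- Cohort: 1/12 = 8.3%, instead of 0/12 = 0%.
- Overall: 1/24 = 4.2%, instead of 0%.
- Common-TEAE table (SAP 4.11.1, more than 5% in any cohort): 8.3% > 5%, so one subject is enough to enter the term. Since 1/n exceeds 0.05 for every n below 20, this is true of any single TEAE in a cohort of 12, not only of a misclassified one.

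**The case against.** The strongest reply is that the SAP already covers the case. The general rule comes first, addresses missing dates and exempts events with clear evidence of a pre-dose start, which an end date before dosing supplies. A reader might infer that the SAP definitely counts every unknown-start event as treatment-emergent. The documents do not support that, because no text gives the specific rule precedence. This part stands, and it is why the point is a conflict between two rules. It does not remove the need for a correction, since the text equally fails to give the general rule precedence.

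The second reply is rarity. Recording starts at consent, at most 14 days before dosing, and the SAP sends pre-existing conditions to medical history unless they worsen. The month or year of onset will usually be known, which makes the date partial and not completely unknown. Protocol 15.1 requires missing data to be explained and provides for queries. Protocol v3.0 section 9.2 confines subjects from the evening of Day -1 to Day 18, although that does not cover the earlier screening days. This stands: few records will be affected.

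Third, defaulting to treatment-emergent is a cautious choice for safety tables. That is fair where timing is truly unknown, but not where the end date settles it. Every event is also listed with its end date, so a misplaced one would be visible.

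A reader might also infer that counts of drug-related events would be inflated. The documents do not support this. Protocol 14.6 lists temporal plausibility first among the features supporting causality, and an event that ended before any drug was given fails it. Nor can one say that the period column is left to the programmer. The SAP's revision history refers to table shells that are not among the documents, and they may settle it.

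**Conclusion.** The point holds as an internal inconsistency in SAP v2.0 section 3.2.3.1. The unknown-start rule, read literally, can classify as a TEAE an event that the SAP's own definition makes a PTAE, and it lacks the end-date test that section 4.8 applies to medications. Whether the error would occur depends on which of the two rules is applied, and the SAP does not say.

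The importance is minor. Each affected subject adds at most 8.3% to a line of a cohort table, assuming 12 dosed subjects and no other event on that line. The number of such events cannot be estimated from the documents but should be very small. The primary pharmacokinetic analysis is untouched. The missing period assignment is a detail for the sponsor to state; no particular convention follows from the documents.

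**What to change.** Make the unknown-start rule conditional. Suggested text: *An AE with a completely unknown start date is treatment-emergent unless its end date (complete, or partial but clearly earlier) is before the first dose, in which case it is a PTAE.* This removes the conflict with the general rule and brings section 3.2.3.1 into line with section 4.8.

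Add one sentence saying which period column takes the remaining unknown-start TEAEs. The choice is the sponsor's. Any convention can misplace some events: sending everything still ongoing at Day 8 to the multiple-dose period, for example, would misplace an event that began on Day 2 and ended on Day 10.

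The cost is one clause and one sentence, plus the matching line of code. No new data are needed, because AE end dates are already collected and listed. SAP section 1 allows updates before database lock and a documented modification request after it. SAP v2.0 is also still based on Protocol v2.0 while v3.0 is current, so an alignment revision would be a convenient occasion.
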